An early placebo-controlled study showed that nabilone, a synthetic THC, dramatically reduced anxiety in anxious patients⁹⁶. These anxiolytic effects of eCB enhancers have sparked interest in CB1 receptors as a pharmacological target for treating anxiety disorders⁹⁷⁻¹⁰⁰. Given that extinction retention deficits and vmPFC-HPC dysfunction have been observed in patients with PTSD, and that enhancing cannabinoid transmission helps extinction recall, the cannabinoid system is a promising target for improving the learning that goes on in therapy and perhaps increasing the efficacy and durability of PE in treating PTSD (e.g., shortening treatment while strengthening and prolonging gains). However, direct tests of cannabinoid effects on extinction recall and associated neural circuits have not yet been conducted in PTSD patients. Therefore, the primary goal of the proposed project is to test the hypotheses that administration of an exogenous CB1 agonist will 'rescue' deficits in fear extinction recall in PTSD patients and that these effects will be mediated by increased activation and functional connectivity of vmPFC and HPC.

To address the issues mentioned above we propose the following specific aims:

Specific Aim 1: To assess the effects of THC on extinction memory recall and vmPFC and HPC activation and connectivity in controls (healthy controls, HC; trauma-exposed non-PTSD controls, TEC).

Hypothesis 1A: Relative to PBO, THC will decrease SCRs and US expectancy ratings to a CS that was previously extinguished (CS+E) during an extinction recall test in controls. Hypothesis 1B: Relative to PBO, THC will enhance regional activation in the vmPFC and HPC to the CS+E during an extinction recall test in controls.

Hypothesis 1C: Relative to PBO, THC will increase functional coupling between the vmPFC and HPC to the CS+E during an extinction recall test in controls.

Specific Aim 2: To compare extinction memory recall success and vmPFC and HPC activation and connectivity between PTSD patients and controls (HC/TEC).

Hypothesis 2A: Relative to controls, PTSD patients will show increased SCRs and US expectancy ratings to the CS+E during an extinction recall test.

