C.4.1. fMRI Analysis: Functional data will be processed and analyzed using conventional methods (GLM, event-related design, random effects) with Statistical Parametric Mapping (SPM8; Wellcome Department of Cognitive Neurology, London; www.fil.ion.ucl.ac.uk/spm)¹⁴⁴⁻¹⁴⁷, previously described in our pharmacological fMRI studies^{91,94,148,149} and extinction recall studies^{102,105}. Analysis will implement 2 complementary approaches⁹⁴: 1) a hypothesis-driven anatomically-focused region of interest (ROI)-based analysis; and 2) exploratory whole-brain voxel-wise analysis. Based on our hypotheses, our two main ROIs are vmPFC and HPC; the AMYG, or at least different sub-regions within AMYG, are involved in fear acquisition^{26,36,150} and extinction²⁵, and thus we identify the AMYG as an ROI *a priori*. These anatomically-defined atlas-based ROIs will be based on anatomical landmarks from human atlases¹⁵¹⁻¹⁵³. In addition, vmPFC and HPC activation reported by Milad et al.⁷⁰ will be used to create a 5 mm radius spherical ROI around peak coordinates to examine data in this study for replication. Extracted BOLD percent signal change (PSC) from each ROI, confined to anatomically-based masks, will be subjected to a repeated measures group (PTSD, TEC, HC) x drug (THC, PBO) x stimulus (CS+E, CS+U) omnibus ANOVA during Extinction Recall. We will test for significant ($p < 0.05$) group x drug x stimulus; all significant main effects and interactions will be followed up by post hoc t-tests with an alpha level of 0.05, two-tailed. If appropriate, we will also include age, gender, and other variables (e.g., mood effects) as additional potential covariates in a separate ANCOVA. For the second approach (whole-brain, voxel-wise), we will employ the same ANOVA approach across the entire brain to search for effects in other areas in an exploratory search to generate hypotheses for subsequent study. Statistical maps for the whole brain analysis will be created using a threshold of $p < 0.001$ with a cluster threshold of 10 voxels. Within the ROIs, a small volume threshold ($p < 0.05$, corrected for multiple comparisons) will be used.

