The context-dependent renewal of fear is another factor that can potentially affect the efficacy of exposure therapy. Therefore, the analysis will also test whether THC can induce generalization of extinction across extinction recall (ABB) and renewal (ABA) contexts. We will conduct the same statistical tests on extracted PSC from each ROI, confined to anatomically-based masks, during the Fear Renewal test, as described above for the Extinction Recall test.

We will also look at correlations between BOLD responses in the AMYG, vmPFC, and HPC and the extinction retention index (see below) during Extinction Recall and Fear Renewal tests. In addition, we will implement psychophysiological interaction analyses (PPI)^{40,154,155} to measure task-dependent functional connectivity among the AMYG, vmPFC, and HPC. Separate connectivity analyses will be performed with each group x drug condition (PTSD-THC, PTSD-PBO, HC-THC, and HC-PBO), using vmPFC and HPC as the seed regions followed by between-group connectivity analyses to assess the effect of THC on functional coupling of the vmPFC, AMYG and HPC during Extinction Recall and Fear Renewal.

C.5. Psychophysiology: The primary assessment of fear learning will be a change in SCR, which will be recorded by electrodes attached to the middle phalanges of the second and third digits of the nondominant hand. AcqKnowledge software (BIOPAC Systems) will be used for off-line analysis. We will also obtain subjective US expectancy to the CS+E compared to the CS+U¹⁰³.

C.5.1. Psychophysiological Analysis: SCR for each CS trial will be calculated as described by Milad et al.¹⁰². Extinction recall will be assessed by comparing the mean differential response during the first four trials of the CS+E versus the first four trials of the CS+U. In addition, we will use the “extinction retention index” (ETI) as described by Milad et al.¹⁰² to measure the magnitude of extinction retention. The ETI adjusts the SCR during extinction recall for differences in CR magnitude during acquisition¹⁰⁹. Analyses will be conducted by ANOVA models as above (follow-up t-tests, $\alpha < 0.05$). In addition, we plan to compare and correlate (using Pearson or Spearman rank Correlational analyses) measures of BOLD activation (PSC) and SCR signal to the CS+E vs. CS+U within and across the two contexts/recall and renewal tests.

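### The primary goal claims mediation by vmPFC and HPC, but no planned analysis estimates an indirect effect, adjusts the brain-behaviour link for drug and diagnosis, or ties connectivity to recall

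*Combined protocol and SAP*

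**What the plan says.** The closing paragraph of section A, before the specific aims, sets the primary goal: to test that a CB1 agonist rescues deficient extinction recall in PTSD patients and that "these effects will be mediated by increased activation and functional connectivity of vmPFC and HPC". Hypotheses 1A to 3C then state separate drug or group effects on SCR and expectancy, on activation, and on coupling. None states an indirect effect.

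The analysis sections plan four things:

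- Drug effect on activation (C.4.1): a "repeated measures group (PTSD, TEC, HC) x drug (THC, PBO) x stimulus (CS+E, CS+U) omnibus ANOVA during Extinction Recall", applied to ROI signal.
- Drug effect on connectivity (C.4.1): PPI by condition, "followed by between-group connectivity analyses to assess the effect of THC on functional coupling of the vmPFC, AMYG and HPC".
- Drug effect on SCR and the retention index (C.5.1): "Analyses will be conducted by ANOVA models as above".
- Brain-behaviour link: "We will also look at correlations between BOLD responses in the AMYG, vmPFC, and HPC and the extinction retention index" (C.4.1), and "we plan to compare and correlate (using Pearson or Spearman rank Correlational analyses) measures of BOLD activation (PSC) and SCR signal" (C.5.1).

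The only covariate model is optional: "we will also include age, gender, and other variables (e.g., mood effects) as additional potential covariates in a separate ANCOVA". It does not name BOLD as a predictor of recall. Section C.1 states that psychophysiology is recorded simultaneously with scanning at extinction recall.

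**The concern.** Mediation needs three things from the data: a drug effect on the candidate mediator, an association of the mediator with the outcome given drug, and an estimate of the product of the two. The plan supplies the first, plus the total drug effect on recall. It does not supply the second or the third.

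A plain correlation does not fill the gap. If THC moves both BOLD and SCR, the two measures correlate across arms even when they are unrelated within each arm. The correlation is therefore least informative about mechanism when the trial's other hypotheses succeed. For connectivity, which the goal names alongside activation, no analysis reaches recall at all. At stake is the mechanistic part of the stated goal. The randomised comparisons of THC with placebo are unaffected.

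**Working it through.** **The plan's own power figure.** C.6 claims more than 90% power with 15-20 usable subjects per cell and cites d = 0.8-1.5. A two-sided t-test at 0.05 between two cells has these properties:

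- At d = 0.8, power is 0.56 (n = 15) to 0.69 (n = 20).
- At d = 1.5, power is 0.98 to 0.996.
- Reaching 90% needs d of about 1.23 (n = 15) or 1.05 (n = 20).
- With all groups pooled (45-60 per drug arm), power at d = 0.8 is 0.96 to 0.99.

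So the figure is reached only at larger effects or with groups pooled. The present point does not depend on it. What matters here is that C.6 gives no power for an indirect effect.

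**Inputs for the check.** From the documents: d = 0.8-1.5 and 15-20 per cell (C.6), 120 usable subjects (D.1), half of the participants on dronabinol (C.3.3.1), and alpha 0.05 two-tailed (C.4.1, stated there for follow-up t-tests). Assumed: drug arms combined without adjustment, the same standardised shift d in both measures, within-arm SD of 1, and zero within-arm correlation. Signs are ignored, because the hypothesised directions (activation up, SCR down) only make r negative.

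**Induced correlation.** With two equal arms, the shift adds d²/4 to each variance and d²/4 to the covariance, so r = (d²/4)/(1 + d²/4).

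- d = 0.8: 0.16/1.16 = 0.138
- d = 1.5: 0.5625/1.5625 = 0.360

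**Chance that it is significant.** By Fisher z, the test statistic has mean atanh(r) × √(N − 3) and SD 1, and is compared with ±1.96. For example, at d = 0.8 and N = 120: 0.1388 × √117 = 1.50, giving 32%. At d = 1.5 and N = 40: 0.3769 × √37 = 2.29, giving 63%. A simulation with fixed equal arms (20,000 runs) gives nearly the same figures:

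| N | d | Fisher z | Simulation |
|---|---|---|---|
| 30 (one group, 15 per arm) | 0.8 | 11% | 12% |
| 40 (one group, 20 per arm) | 0.8 | 13% | 14% |
| 120 (all cells) | 0.8 | 32% | 32% |
| 30 | 1.5 | 50% | 54% |
| 40 | 1.5 | 63% | 67% |
| 120 | 1.5 | 98% | 99% |

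In the same simulations, a test requiring both a drug effect on the mediator and a drug-adjusted mediator effect on the outcome stayed at or below 5% throughout.

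**What the adjusted test could detect.** If mediation is real, with an assumed drug-adjusted slope of 0.3-0.5 (not in the documents) and d = 0.8-1.5, its power is 18-69% at N = 30, 30-83% at N = 40, and 88-99.9% at N = 120 with groups combined.

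**The case against.** The strongest reply is that the aims, not one causal word in the background, define what is tested. Section A says the aims address the issues raised, and each hypothesis is a separate effect that the ANOVAs and PPI comparisons do test. That stands, and it limits the point in several ways.

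- A reader might infer that the plan rests on correlations alone, or that half of the primary goal goes unanswered. Neither is supported. The drug-to-brain and drug-to-recall effects are tested; what is missing is the drug-adjusted brain-to-recall path and the indirect effect.
- A reader might infer that the correlations are pooled over arms. The plan does not say. It names the method ("using Pearson or Spearman rank Correlational analyses") and covers analyses within and across contexts and tests, which is not the same as within drug arm. The percentages apply only if arms are combined unadjusted. Correlations within each arm would avoid the artefact but would still supply only one path.
- The equal-shift set-up is a simplification. C.6 ties its effect sizes to imaging signals and gives none for SCR or the retention index. The N = 120 rows also assume the same drug shift in every group and no diagnosis difference, whereas Aim 2 expects diagnosis differences. The goal concerns PTSD patients, so N = 30-40 is the closest case, and at d = 0.8 the figure there is only 12-14%.
- A reader might infer that the sponsor will present a significant correlation as proof of mechanism. Nothing in the documents says so; the correlations are introduced as additional analyses.

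**Conclusion.** The point holds as a gap between a stated goal and the analyses listed for it. The plan estimates no indirect effect, states no adjustment of the brain-behaviour association for drug or diagnosis, and has no analysis linking PPI coupling to recall. Under the assumptions above, an unadjusted correlation with nothing behind it is significant in about 12-14% (N = 30-40) to 32% (N = 120) of trials at d = 0.8, and in about 54-67% to 98-99% at d = 1.5. It therefore cannot distinguish mediation from parallel drug effects.

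It is also tempting to conclude that an indirect-effect interval excluding zero would justify the word 'mediated'. The design does not support that. BOLD and SCR are recorded at the same time, so their order is not established, and only the drug is randomised, so mediator-outcome confounding remains. The matter should be put right, but it does not touch the validity of the randomised drug comparisons.

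**What to change.** In C.4.1 and C.5.1, specify the brain-behaviour analyses as a regression of the retention index or SCR on ROI percent signal change, and separately on vmPFC-HPC PPI, with the six-level group-by-drug cell as a factor. Combine the mediator coefficient with the drug effect on the mediator, and report that indirect effect with a bootstrap confidence interval. Label it exploratory, say how many ROI and PPI mediators are examined, and state that simultaneous measurement leaves order and mediator-outcome confounding unresolved. PPI estimates will be needed in all six cells; the conditions listed in C.4.1 name only the PTSD and HC cells.

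In section A, change 'will be mediated by' to 'will be accompanied by', whatever the interval later shows.

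No new data are needed. The cost is a little more analysis, a more modest claim, and an indirect effect that will be imprecise at 15-20 per cell.

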Hypothesis 2B: Relative to controls, PTSD patients will show attenuated regional activation in the vmPFC and HPC to the CS+E during an extinction recall test. Hypothesis 2C: Relative to controls, PTSD patients will show less functional coupling between the vmPFC and HPC to the CS+E during an extinction recall test.

Specific Aim 3: To investigate whether THC can correct extinction memory recall impairments and aberrant vmPFC and HPC activation and connectivity in PTSD patients.

Hypothesis 3A: Relative to PBO, THC will decrease SCRs and US expectancy ratings to the CS+E during an extinction recall test in PTSD patients, similar to levels observed in controls (HC/TEC). Hypothesis 3B: Relative to PBO, THC will enhance regional activation in the vmPFC and HPC to the CS+E during an extinction recall test in PTSD patients, similar to controls (HC/TEC). Hypothesis 3C: Relative to PBO, THC will increase functional coupling between the vmPFC and HPC to the CS+E during an extinction recall test in PTSD patients, similar to extent of connectivity observed in controls (HC/TEC).

B. Preliminary Data

The preliminary data here: 1) establish the capacity of the PI to carry out fMRI studies of fear extinction learning and THC challenge in humans; 2) provide evidence that THC facilitates extinction recall in healthy humans; and 2) provides evidence collected by the PI that replicate findings of extinction recall deficits in PTSD patients and support the hypotheses and feasibility of the proposed study.

Impaired Extinction Recall and Dysfunction Activation of vmPFC and HPC during Extinction Recall in PTSD

To assess fear extinction recall in PTSD, Milad and colleagues have developed a fear conditioning-extinction paradigm and has shown less activation in vmPFC and HPC and increased SCRs in PTSD patients (vs. trauma-exposed non-PTSD controls) during extinction recall in response to the a previously extinguished CS+ (CS+E) compared to a non-extinguished CS+ (CS+U)⁷⁰. The PI has collected SCR data as a measure of fear in healthy controls (HCs; n = 15) and PTSD patients (n = 14) in a behavioral pilot study of fear extinction learning and recall using the study design proposed here. Similar to Milad et al.⁷⁰, when recall of extinction was tested 24 hours after extinction learning PTSD patients exhibited recovery of fear, as evidenced by increased SCRs

[figure not shown]

Fig. 2: Deficits in extinction recall in PTSD

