This fMRI protocol adopts a similar event-related design developed and validated by Milad et al.^{101,102}, which manipulates context using an ABBA design and will be conducted over 4 study visits. Stimulus parameters will be similar to those conducted by Milad et al.¹⁰². Each “context” will consist of different images of a neutral scene in which the conditioned stimuli will appear. Conditioned stimuli (CSs) will consist of emotionally neutral objects or facial expressions and unconditioned stimuli (US) will be an adverse stimulus (e.g. loud noise¹⁰³; a mild electric shock to the wrist^{36,101,102,104-110}). During all sessions, our primary measures of conditioned fear will be measures of psychophysiological responding via electrodes, as well as US expectancy ratings for each CS trial¹⁰³. All experimental phases (Extinction, Extinction Recall/Fear Renewal), except Fear Acquisition, will be conducted in the fMRI scanner with simultaneous psychophysiological recordings and US expectancy ratings. Fear Acquisition will be conducted in one our testing rooms at the Eugene Applebaum College of Pharmacy & Health Sciences (EACPHS) building.

C.2. Nature of Participant Population: The number of participants expected to participate in the study is 150 [50 patients with PTSD and two controls groups individually matched (age, gender, education): 50 trauma-exposed subjects without PTSD (also matched on trauma-exposure) and 50 non-exposed subjects]. The sample size is required to reach at least 15-20 participants in each experimental group (6 groups). Based on prior experience we expect that data from about 30 participants (5 per group) will be not be usable due to either failure to complete all sessions or poor skin conductance recordings. Participants of both genders will be included in the study and the age range of participants will be from 21-45. Persons below 21 or above 45 are excluded because beyond this range age may influence response to the drugs. Furthermore, the relatively small age range is intended to reduce variation in performance on the behavioral task. There are no enrollment restrictions based upon race or ethnic origin. Candidates will undergo a structured clinical psychiatric interview¹¹¹⁻¹¹³ and will fill out questionnaires related to their general physical health, current medications, with a detailed section on current and lifetime drug and alcohol use.

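### The control reference for PTSD conclusions differs between the aims (HC/TEC), the ANOVA (three groups) and the connectivity analysis (HC only), and no deciding contrast is named

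*Combined protocol and SAP*

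**What the plan says.** The control reference appears in three forms.

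- **Aims (section A).** Specific Aim 2 is "To compare extinction memory recall success and vmPFC and HPC activation and connectivity between PTSD patients and controls (HC/TEC"). Hypothesis 2A reads "Relative to controls, PTSD patients will show increased SCRs and US expectancy ratings to the CS+E during an extinction recall test", and 2B and 2C use the same undivided comparator. Hypothesis 3A sets the target for THC as "similar to levels observed in controls (HC/TEC"), and 3B and 3C follow it.
- **ROI and SCR analyses (C.4.1, C.5.1).** Extracted signal goes into a "repeated measures group (PTSD, TEC, HC) x drug (THC, PBO) x stimulus (CS+E, CS+U) omnibus ANOVA", and "all significant main effects and interactions will be followed up by post hoc t-tests with an alpha level of 0.05, two-tailed". For skin conductance, "Analyses will be conducted by ANOVA models as above". The t-tests are not named.
- **Connectivity (PPI paragraph of C.4.1).** The group-by-drug conditions listed are PTSD and HC, each on THC and on placebo. The two TEC cells are absent, although C.6 lists all six cells.

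C.2 shows how the control groups differ. It plans "50 trauma-exposed subjects without PTSD (also matched on trauma-exposure) and 50 non-exposed subjects", next to 50 patients with PTSD.

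**The concern.** HC differ from the patients in two respects, trauma exposure and diagnosis. TEC are matched on the first. A comparison of PTSD with HC, or with a mixture of HC and TEC, therefore carries some effect of exposure along with any effect of the disorder.

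Hypotheses 2A-2C are worded so that a difference from undivided controls would confirm them. If trauma exposure without PTSD changes extinction recall, vmPFC or HPC activation, or their coupling, the trial could report a PTSD deficit that is partly or wholly an exposure effect. With no contrast named in advance, the choice among PTSD-TEC, PTSD-HC and PTSD-pooled can be made after the results are seen.

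The exposure is most direct for Hypotheses 2C and 3C, because the connectivity analysis as listed has no exposed control group.

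**Working it through.** **Sample size, reproduced first.** C.2 enrols 150 and expects that "data from about 30 participants (5 per group) will be not be usable". So 150 - 30 = 120 usable, as D.1 states, and 120 / 6 = 20 per cell. C.2 and C.6 give a range of 15-20 per cell.

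**What each reference estimates.** Let P, T and H be the PTSD, TEC and HC means, with equal numbers of TEC and HC.

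- PTSD versus TEC: P - T.
- PTSD versus pooled controls: P - (T + H)/2 = (P - T) + ½(T - H).
- PTSD versus HC: P - H = (P - T) + (T - H).

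The share of the TEC-HC difference that enters is zero, one half and all of it, respectively.

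**What that could do to error rates.** The documents give no TEC-HC difference, so 0.3, 0.5 and 0.8 SD are assumptions. Set P = T, unit SD, two-sided t-test at 0.05. Percentage of simulated trials with a significant PTSD effect:

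| TEC-HC (assumed) | Pooled, 20 vs 40 | HC only, 20 vs 20 | TEC, 20 vs 20 |
|---|---|---|---|
| 0.3 SD | 8% | 15% | 5% |
| 0.5 SD | 14% | 34% | 5% |
| 0.8 SD | 27% | 69% | 5% |

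With 15 per cell, the pooled figures are about 7%, 11% and 20%, and the HC-only figures 12%, 26% and 56%. Over both drug arms (40 PTSD against 80 or 40 controls), they are about 11%, 23% and 49% pooled, and 26%, 60% and 94% against HC alone.

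**The three-group ANOVA.** Simplify the C.4.1 group effect to a one-way F test on a unit-SD score, 20 per group, with the same assumptions.

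- F significant and then PTSD-TEC significant: about 3%, 4% and 5% at 0.3, 0.5 and 0.8 SD.
- F significant and then PTSD-HC significant: about 26% at 0.5 SD.

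The planned sequence protects the conclusion if PTSD-TEC is the follow-up that counts, and does not if PTSD-HC is accepted.

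**Power of the named contrast.** Take d = 0.8, the low end of the range in C.6. The noncentrality is d·√(n₁n₂/(n₁+n₂)), with n₁+n₂-2 degrees of freedom.

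| Comparison | Noncentrality | Power |
|---|---|---|
| PTSD vs TEC, 20 vs 20 | 0.8·√10 = 2.53 | 69% |
| PTSD vs pooled, 20 vs 40 | 0.8·√13.33 = 2.92 | 82% |
| PTSD vs TEC, 40 vs 40 | 0.8·√20 = 3.58 | 94% |
| PTSD vs pooled, 40 vs 80 | 0.8·√26.67 = 4.13 | 98% |

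At 15 per placebo cell the powers are 56% and 70%. The rows over both drug arms assume the same difference of 0.8 on THC and on placebo. Aim 3 expects THC to shrink that difference, so the placebo-cell rows are the safer guide.

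**The case against.** The strongest reply is that the analysis plan never pools the controls. C.2 describes two control groups, C.4.1 has a three-level factor, C.5.1 adopts the same models, and C.6 counts six cells. The label HC/TEC may simply mean HC and TEC. This stands: a reader might infer from the aims that a PTSD versus HC+TEC test is planned, but no section specifies one. The pooled percentages above describe what such a test would do; they are not error rates of the written analysis. What remains for ROI and SCR is that the deciding contrast is unnamed.

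A reader might also infer that the control reference undermines the drug effect in Aim 3. It does not. THC versus placebo within PTSD is a randomised comparison and needs no controls. Only the benchmark of similarity to controls depends on them, and non-exposed healthy function is a defensible target as well as TEC.

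Three further points are fair.

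- No section says why TEC were recruited. That they serve to separate exposure from PTSD is an inference from the matching.
- PTSD equal to TEC is a worst case. Section B cites an earlier fMRI study that found deficits in PTSD against trauma-exposed controls. If TEC recalled extinction better than HC, pooling would understate a PTSD deficit.
- PTSD versus TEC does not isolate the disorder completely. C.3.1.4 allows past depression or substance disorder, and under a condition psychoactive medication, in the PTSD group, while TEC must be free of lifetime Axis I and II disorders.

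None of these supplies the missing contrast or puts TEC into the connectivity list. The investigator's own SCR pilot in section B compared PTSD with HC only, so it cannot settle the exposure question.

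**Conclusion.** The point holds as an inconsistency with consequences for interpretation. The aims, the ANOVA and the connectivity analysis use three different control references, and none is declared decisive for a PTSD conclusion. For ROI and SCR, the data and model can answer the question, but the plan does not commit to the contrast that does. For connectivity as listed, HC is the only control, so the whole of any TEC-HC difference enters Hypothesis 2C and the benchmark in 3C.

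The shares of one half and all are algebra and need only equal numbers of TEC and HC. The percentages rest on assumed TEC-HC differences, on no true PTSD-TEC difference and on 20 usable subjects per cell. They show scale and do not predict this trial. The randomised THC effect within PTSD is unaffected.

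**What to change.** 1. In Specific Aim 2, C.4.1 and C.5.1, name PTSD versus TEC as the contrast that decides Hypotheses 2A-2C. State whether it is taken in the placebo cells or over both drug arms.
2. Report TEC versus HC separately as the trauma-exposure effect, and PTSD versus pooled controls as supportive.
3. Add the TEC-THC and TEC-PBO cells to the connectivity analysis.
4. For Aim 3, keep THC versus placebo within PTSD as the test, and report the comparison with controls against TEC and HC separately.

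The change is to wording and contrasts; TEC are already being recruited, so no new data are needed. The cost is power relative to a pooled test that the analysis sections do not specify: at d = 0.8, 13 percentage points with 20 per placebo cell (82 - 69), and 4 over both drug arms (98 - 94). The 69% is also below the more than 90% claimed in C.6, which does not name its test, so C.6 should state the power of the named contrast.
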